Aim 1: Determine the relationship between added sugars (% calories) intake during pregnancy and infancy/toddlerhood (birth to 24 months) on brain structure and function.

Aim 2: Determine the relationship between fructose (% calories) consumption during pregnancy and infancy/toddlerhood (birth to 24 months) on brain structure and function.

Secondary Aims:

Secondary Aim 1: Determine the relationship between added sugars (% calories) intake during pregnancy and infancy/toddlerhood (birth to 24 months) on cognition.

B. Study Type and Design: This is a non-interventional, observational study.

Added sugar intake during pregnancy will be assessed using dietary data collected between 12-20 wks gestation using the National Cancer institute (NCI) DHQ-II food frequency questionnaire (FFQ) or three 24-hour dietary recalls.

Offspring dietary intake was collected at 2 weeks and at 6, 12, and 24 months by one multiple-pass 24-hour dietary recall administered to the child's caregiver and collected by trained research staff.

For the present study, we will collect three total dietary recalls: two weekday and one on the weekend.

Brain structure and function will be measured using MRI and EEG assessments. Cognition will be measured using dimensional change card sort task and Peabody picture vocabulary test.

C. Sample size, statistical methods, and power calculation

1. n/a – randomization will not be used
2. n/a – study will not be blinded
3. The present study is pilot. The planned sample size is 45 subjects.

D. Subject Criteria (See Vulnerable Populations appendix, if applicable): Participants who were previously enrolled in the ADORE GAINS study will be invited to participate in the present study when they are 5-6 years old. Participants will be both male and female and English or Spanish speaking.

1. Inclusion criteria: Participated in ADORE GAINS. Age 5-6.
2. Exclusion criteria: children who have received an autism diagnosis (per parent report)
3. Withdrawal/Termination criteria: n/a

4. Subjects may enter another research study while participating in this research study, as this study is observational only.

E. Specific methods and techniques used throughout the study

1. Laboratory tests: n/a
2. Study Procedures:

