D. Procedures to protect subject confidentiality: There is no appreciable risk of loss of confidentiality. Subjects will be made aware of persons who may see their protected health information in the informed consent document and may choose not to enroll in the study based on the information provided them in accord with 2003 HIPAA regulations. The patient's confidentiality will be maintained and will not be made publicly available to the extent permitted by the applicable laws and regulations.

E. Quality Assurance / Monitoring

1. All data entry will be verified by a second study team member using the original source document to ensure data are accurate, consistent, complete and reliable.
2. n/a – no plans to have ongoing third-party monitoring

V. Data Analysis and Reporting

A. Statistical and Data Analysis: The data analysis plan for each primary aim is described below. There are no planned interim analyses.

1. **Aim 1 analysis:** Determine the relationship between added sugars (grams and % calories) intake during pregnancy and infancy/toddlerhood (birth to 24 months) on brain structure and function. Brain structure will be quantified as brain volume in Freesurfer. Based on prior studies, we will examine the Pearson correlation between hippocampal brain volume and added sugars intake during pregnancy and infancy/toddlerhood. Exploratory analyses will examine correlations with added sugars intake and brain volume in inhibitory control brain regions (i.e., dorsal anterior cortex) and reward related regions (i.e., ventromedial prefrontal cortex). Brain function will be quantified as resting state functional connectivity within the default mode network which includes prefrontal and parietal regions as well as the attention and salience networks. Pearson correlations will examine the relationship between functional connectivity metrics and added sugars intake. Brain function during the EEG Food Go/NoGo task will be quantified as the amplitude of the P3 and N2 components and correlations will examine the relationship between P3/N2 amplitudes and added sugars. Analyses will be corrected for multiple comparisons using a Bonferroni correction.

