2. **Aim 2 analysis:** Determine the relationship between fructose (grams and % calories) consumption during pregnancy and infancy/toddlerhood (birth to 24 months) on brain structure and function. As in Aim 1 analyses, brain structure will be quantified as Freesurfer volumes, brain function will be quantified as resting state connectivity, and brain activation during the EEG Food Go/NoGo Task. Correlations will be used to examine the relationship between brain measures and fructose consumption.

B. Outcome: We hypothesize that added sugars and fructose intake will be negatively related to brain structure (hippocampal volume) and function (resting state functional connectivity and P3 amplitude). The strength of the correlations and level of significance will determine if there is a relationship between variables being tested.

C. Study results to participants: Study participants will be informed of the overall study results via a letter, which will be mailed after the study and analysis is complete. Participants will not be given their individual results from study procedures; however, this information may be made available upon request, with approval by the PI.

D. Publication Plan: The present study is a pilot. This project was submitted as a June 2022 R01 and received positive reviews. It will be resubmitted in November 2022 with the hope of receiving R01 funding to extend the study to the entire ADORE GAINS cohort. We hope by getting more participants to complete the cognitive tests and body composition measurements that we will have a large enough sample to publish results relating to those

measurements. Any publications would further support the R01 application.

VI. Literature Cited

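### Prenatal added sugar intake may come from either of two dietary instruments, and the planned correlations contain no term for which one was used

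*Combined protocol and SAP*

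**What the plan says.** All references are to the combined protocol and SAP.

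- **Prenatal exposure (II.B).** Intake is taken from data collected at 12-20 weeks of gestation, "using the National Cancer institute (NCI) DHQ-II food frequency questionnaire (FFQ) or three 24-hour dietary recalls". The section gives no number per instrument, no account of what decided it, and no calibration between the two.
- **Offspring exposure (II.B).** "Offspring dietary intake was collected at 2 weeks and at 6, 12, and 24 months by one multiple-pass 24-hour dietary recall". One method is used throughout, so only the prenatal exposure is affected.
- **Size (II.C).** "The planned sample size is 45 subjects", described as a pilot. No alpha, power or effect size is stated.
- **Aim 1 analysis (V.A.1).** The exposure is in two units: "Determine the relationship between added sugars (grams and % calories) intake during pregnancy". The structural analysis is the "Pearson correlation between hippocampal brain volume and added sugars intake during pregnancy" and infancy/toddlerhood. The functional outcomes are also handled by correlation. "Analyses will be corrected for multiple comparisons using a Bonferroni correction"; the number of tests is not given.
- **Aim 2 analysis (V.A.2).** "Correlations will be used to examine the relationship between brain measures and fructose consumption".
- **Decision (V.B).** "The strength of the correlations and level of significance will determine if there is a relationship between variables being tested".

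No covariate, stratum or calibration for instrument appears. Sex is the only modifier named (I.A), as an exploratory question.

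**The concern.** A food frequency questionnaire and a set of 24-hour recalls are different measuring devices and need not give the same mean for the same diet. If some mothers have one and some the other, a plain correlation pools the two scales and treats any mean difference between them as a difference in intake.

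What follows depends on whether instrument group is related to the brain measure. If it is not, the offset is noise in the exposure: the correlation shrinks and type I error stays nominal. If it is, for example because instrument tracked enrolment period or language, the offset confounds the correlation. It can then create an association, mask one or exaggerate one. V.B rests the conclusion on the strength and significance of these correlations, so either effect would reach it. The study also sets out to compare exposure windows, and only the prenatal window is open to this problem.

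**Working it through.** **Inputs from the documents:** n=45 (II.C); plain correlation, no instrument term (V.A). There is no stated power calculation to reproduce.

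**Assumed, because the documents give no values:** two-sided alpha 0.05; correlation within instrument ρ = 0.40 in size; share p on one instrument; offset d between instruments, in within-instrument SD; outcome difference g between instrument groups, in within-group SD. Write v = p(1-p). Power uses Fisher's z: atanh(r) × √(n-3), compared with 1.96. With the indicator, n-4 replaces n-3.

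**1. No offset.** atanh(0.40) = 0.42365. Unadjusted: 0.42365 × √42 = 2.746, power 78.4%. With the indicator: 0.42365 × √41 = 2.713, power 77.4%.

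**2. Instrument unrelated to the outcome (g=0).** Observed r = 0.40/√(1 + v d²).

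| Split | v | d=0.5: r, power | d=1.0: r, power |
|---|---|---|---|
| 50:50 | 0.25 | 0.388, 75.6% | 0.358, 67.9% |
| 20:80 | 0.16 | 0.392, 76.6% | 0.371, 71.5% |
| 10:90 | 0.09 | 0.396, 77.4% | 0.383, 74.4% |

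Under the null, simulated rejection at d=0.5 and 50:50 is 5.1%, so type I error is unaffected.

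**3. Instrument related to the outcome.** Observed r = (ρ + v d g)/√[(1 + v d²)(1 + v g²)]. Take 50:50 and d = g = 0.5, so v d g = v d² = v g² = 0.0625.

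- No true association: r = 0.0625/1.0625 = 0.059. Rejection is 6.7% (6.6% simulated; 5.0% with the indicator).
- True ρ = -0.40, shift opposing it: r = (-0.40 + 0.0625)/1.0625 = -0.318, power about 57%. With the same g and no offset, r = -0.40/√1.0625 = -0.388, power about 76%. With the indicator, simulated power is about 78%.
- True ρ = -0.40, shift reinforcing it: r = (-0.40 - 0.0625)/1.0625 = -0.435, an overstatement.

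At d = 1.0 and g = 0.5 (50:50), null rejection is 10.9%; the indicator returns it to 5.0% in simulation.

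**4. When the indicator pays for itself without confounding.** Break-even is at r = tanh(0.42365 × √(41/42)) = 0.39573, so v d² = (0.40/0.39573)² - 1, about 0.0217. This gives d = 0.29 (50:50), 0.37 (20:80) and 0.49 (10:90).

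**5. Very small groups.** At d=0.5 and g=0, with 5 of 45 on one instrument, v = 5×40/45² = 0.0988 and power is 77.3% unadjusted against 77.4% adjusted. With 4 of 45, simulated power is 78.0% against 77.9%. Power does not separate 4 from 5.

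**6. What the indicator does not repair.** With assumed reliabilities of 0.5 and 0.8 for the two instruments and no offset, a true r of 0.40 appears as about 0.31 with or without the indicator (simulated).

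**The case against.** The strongest reply is that no harm is shown. The wording in II.B fits a mixed set of mothers, but also a single instrument among those who enrol. The children come from an earlier cohort, whose own protocol may say how instrument was assigned. That is correct and stands, and it makes the whole point conditional. A reader might infer that the prenatal correlations are already biased or will give false positives. The documents do not support that: a false positive needs both instruments, a systematic offset and a link between instrument and brain measure, and none of the three is documented.

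Second, the effect is small: under 3 points of power at 0.5 SD. This stands for pure dilution. A reader might extend it to every case with an offset of 0.5 SD or less. That does not follow, because with instrument related to the outcome and the shift opposing a true association the loss is nearly 20 points.

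Third, expressing intake as % calories may reduce an offset. It may, but V.A analyses grams as well.

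Fourth, adjustment costs a little power at small offsets, and a sensitivity analysis might be enough. The cost is real, at about one point. A sensitivity analysis alone would leave the confounded estimate as the one on which V.B decides, so adjustment is preferable when both groups are of reasonable size. With only a handful of mothers on one instrument, the objection holds.

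**Conclusion.** The point holds in conditional form and is minor. The plan allows two instruments for the prenatal exposure and, followed as written, would pool them without a term for the difference. Whether that matters depends on facts the documents do not give.

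Dilution alone is a small loss at offsets up to 0.5 SD and a moderate one (about 10 points of power) at 1.0 SD with a 50:50 split. Confounding by instrument can do more, in either direction, even at 0.5 SD. All of these sizes rest on assumed values of r, split, offset and outcome difference, at two-sided 0.05. The Bonferroni threshold will be lower if more than one test is counted, which lowers every power figure. Severity stays minor because the study is a pilot that states no power.

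**What to change.** In V.A:

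1. Report the number of mothers per instrument and how instrument was decided.
2. Before any correlation is run, prespecify that, if both instruments occur, the prenatal analysis is a partial correlation adjusted for an instrument indicator (FFQ or recalls), with the unadjusted correlation reported beside it.
3. If only a handful of mothers used one instrument, the unadjusted correlation may stay primary, with the adjusted or single-instrument result as a sensitivity analysis. The sponsor should set that cut-off in advance as a matter of judgement; the power figures do not determine it.
4. If all mothers share one instrument, say so and change nothing.
5. Apply the same rule to prenatal fructose if it comes from the same instruments, which the documents do not state.
6. State as a limitation that the indicator removes a mean shift only, not unequal random error.

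The cost is a few sentences and one degree of freedom. Without confounding there is a slight net loss of power at offsets below about 0.3 to 0.5 SD, depending on the split. Any true difference in mean intake between the instrument groups no longer contributes to the estimate. The instrument used for each mother must be retrievable from the earlier cohort's records, which the documents do not confirm.

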Peabody Picture Vocabulary Test (PPVT). Receptive vocabulary will be assessed using the PPVT-4. The PPVT-4 is a nationally standardized assessment of receptive vocabulary that has been shown to be fair with respect to cultural and economic status⁷¹. In this task,

participants are shown pages depicting 4 pictorial choices. For each page, the examiner says a word, and the participant indicates, either by pointing or by stating a reference number, which picture best matches the word. Administration is simple and straightforward. The PPVT-4 yields a standard score normed with a mean of 100 and a standard deviation of fifteen. It takes about 30 minutes to complete.

If one or both cognitive tests (DCCS and PPVT) are not completed at the second study visit for any reason, such as subject fatigue, the study team can ask the family if they are willing to come back at a later date for completion of the test(s). Compensation of an additional \$50 would be provided if an additional visit is completed.

Dual energy x-ray absorptiometry (DXA) scan: (Prodigy, Madison, WI, encore software version 13.60) will be used to measure body composition and regional AT distribution. The DXA is located within the Dietetics & Nutrition Clinic inside the Smith West building at KUMC. Using specific anatomic landmarks as previously described, regions including the arms, legs and trunk will be demarcated⁷². Calculations for FM in each region and summed for regions comprising the central (trunk) and peripheral (arms plus legs) will be completed. If a child moves during the scan the scan may need to be re-done but no more than 2 scans will be given over the duration of the study. The DXA scan takes about 10 minutes.

If there is movement during the first DXA scan and the study team and/or parent does not think the child will lay still for a second scan, the family may be asked if they would come back a different day to complete a second DXA. As stated above, no more than 2 scans will be given over the duration of the study. Compensation of an additional \$50 would be provided if an additional visit to repeat the DXA scan is completed.

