Anthropometry: Body weight will be assessed on a same calibrated scale (Detetco Scales, Webb City, MO). Standing height will be measured using a wall mounted stadiometer (Accu-Hite, Seca Corp, Hanover, MD). Subjects will remove shoes and be centered on the stadiometer. Height will be recorded to the nearest 0.1 cm. Two measurements will be taken and the average will be recorded. The measurements take about 5 minutes to complete.

Skinfolds: Six skinfolds will be measured to represent AT distribution in order to compare to larger trials that do not have DXA. [name] has published using these methods to assess infant FM distribution⁷³ and it has been argued skinfolds are a valid metric of regional FM⁷⁴. All measurements will be collected using standardized procedures to our Laboratory and will take place on the same day as the body composition assessment by DXA using standardized procedures. All skinfolds will be identified using anatomical landmarks and taken on the right side of the body using Lange calipers (Beta Technology, Santa Cruz, CA). Skinfolds will be taken in order from head to toe and then repeated in that same order. If two skinfold measurements differ by more than 1 mm, a third measurement will be taken. The two measurements within 1 mm will be averaged and used for analysis. Biceps and triceps skinfolds will be measured at the midline of the

anterior and posterior surface of the arm, respectively, on the mid-point between acromial process of the scapula and olecranon process of the ulna. Subscapular skinfold will be measured at the lower angle of the scapula. Suprailiac skinfold will be measured anteriorly to the midaxillary line and superiorly to the iliac crest, along the natural cleavage of the skin. The thigh skinfold will be measured at the mid-point between patella (kneecap) and inguinal crease at the anterior surface of the thigh. Flank skinfold will be measured immediately above the iliac crest at the mid-axillary line. Central FM will be calculated by adding the subscapular, suprailiac and flank skinfolds and dividing by two. Peripheral FM will be calculated by adding the thigh, biceps and triceps skinfolds and dividing by three. The skinfolds take about 15 minutes to complete.

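### The central skinfold score divides three sites by two while the parallel peripheral score divides three by three; if a three-site mean is meant, central values are 1.5 times too high

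*Combined protocol and SAP*

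**What the plan says.** All of the operative text is in the skinfold paragraph of protocol section II.E.2 (Study Procedures).

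- Purpose and number of sites: "Six skinfolds will be measured to represent AT distribution in order to compare to larger trials that do not have DXA".
- Repeat readings: each site is read twice, with a third reading if the first two differ by more than 1 mm. Then: "The two measurements within 1 mm will be averaged and used for analysis".
- Two of the central sites have separate landmarks: "Suprailiac skinfold will be measured anteriorly to the midaxillary line and superiorly to the iliac crest" and "Flank skinfold will be measured immediately above the iliac crest at the mid-axillary line".
- Central score: "Central FM will be calculated by adding the subscapular, suprailiac and flank skinfolds and dividing by two".
- Peripheral score: "Peripheral FM will be calculated by adding the thigh, biceps and triceps skinfolds and dividing by three".

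The DXA paragraph of the same section separately derives regional fat mass: "Calculations for FM in each region and summed for regions comprising the central (trunk) and peripheral (arms plus legs) will be completed". Section V.A gives no analysis of skinfold scores. Section V.D (Publication Plan) hopes that "getting more participants to complete the cognitive tests and body composition measurements that we will have a large enough sample to publish results" on those measurements.

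**The concern.** Two consecutive sentences define what look like matching scores, each from three sites, but with different divisors and no explanation. Anyone programming the derivation from the protocol would produce a central score on a different scale from the peripheral one.

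The skinfolds are there to describe how fat is distributed and to allow comparison with trials that have no DXA. Both uses depend on the scale of the score. A child with the same thickness at every site would appear centrally adipose purely because of the divisor. The double data entry check in section IV.E compares entries with source documents. It would not detect a score calculated exactly as the protocol instructs.

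**Working it through.** **Inputs from the protocol (II.E.2, Skinfolds).** Central: three sites, divisor 2. Peripheral: three sites, divisor 3. Total measured: six, which matches 3 + 3. The protocol states a formula and no numerical result, so there is no figure to reproduce. It gives no readings either, so every millimetre value below is an illustrative assumption.

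**Can the divisor of two be explained?**
- *Repeat readings.* These are averaged within a site before the score is formed, so the two is not the replicate average.
- *Suprailiac and flank counted as one site.* Each has its own landmark, and both are needed to reach six.
- *Deliberate weighting.* None is stated, and no other section redefines the score.

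**Size if a three-site mean is intended.** Let S be the sum of the three central sites.

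(S/2) / (S/3) = 3/2 = 1.5 for any S > 0.

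| Central sites (mm, assumed) | S | As written, S/2 | Mean, S/3 | Factor |
|---|---|---|---|---|
| 6, 6, 6 | 18 | 9.0 | 6.0 | 1.5 |
| 8, 7, 9 | 24 | 12.0 | 8.0 | 1.5 |
| 4, 10, 12 | 26 | 13.0 | 8.67 | 1.5 |

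**Central against peripheral.**
- With equal thickness at all six sites (6 mm), the ratio is 9/6 = 1.5 as written and 6/6 = 1.0 with a mean. The central share is 9/(9 + 6) = 0.60 against 6/(6 + 6) = 0.50.
- With central sites 8, 7, 9 and a peripheral mean of 10 mm, the ratio is 12/10 = 1.2 instead of 8/10 = 0.8. The difference is +2 mm instead of −2 mm.
- In general, central as written exceeds peripheral when 1.5 × (central mean) > peripheral mean, that is, when the central mean is more than two-thirds of the peripheral mean.

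**Size if two central sites were meant.** For 8 (subscapular), 7 (suprailiac) and 9 (flank), the score as written is 12.0.
- Subscapular and suprailiac: 15/2 = 7.5; 12.0/7.5 = 1.60.
- Subscapular and flank: 17/2 = 8.5; 12.0/8.5 = 1.41.
- Suprailiac and flank: 16/2 = 8.0; 12.0/8.0 = 1.50.

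The factor now depends on the child. With subscapular 8 and suprailiac 7 as the intended pair (7.5), a flank of 5 gives (20/2)/7.5 = 1.33 and a flank of 12 gives (27/2)/7.5 = 1.80.

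**Effect on correlations.** A constant factor leaves a Pearson correlation of the central score unchanged, and that of a central-to-peripheral ratio as well. A central-minus-peripheral difference is not protected. In one simulated data set of 45 children, r for the central score was 0.306 with either divisor, while r for the difference was 0.161 with divisor two and 0.096 with divisor three. If the site list is what is wrong, the error is not constant and correlations of the central score can change too.

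**Lesser, separate gap: the third reading.** Readings of 10, 12, 11 contain two pairs within 1 mm, (10, 11) and (12, 11), giving 10.5 or 11.5. Readings of 10, 12, 14 contain none. The rule gives no unique value in either case.

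**The case against.** The strongest reply is that little depends on this. Skinfolds appear in no primary or secondary aim (II.A) and no planned analysis (V.A). The site readings are collected, so the score can be rebuilt at any time, and DXA provides a separate regional measure. This stands, and it keeps the point minor. One qualification: skinfolds are planned for the same day as DXA, but section II.E.2 also allows missed skinfolds at a later visit, so same-day DXA is not assured for every child.

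A second objection concerns intent. The text never calls either score a mean. Measuring six sites does not prove that all six enter a score, and suprailiac and flank lie close together. The laboratory's own procedure, on which the paragraph relies, is not reproduced. This stands in part: the 1.5 is conditional, and the protocol alone cannot settle which element is wrong. It does not remove the inconsistency, because the sentence as written is neither a three-site nor a two-site mean.

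Third, the comparison with other trials is attached to the six skinfolds, not expressly to the composite, so individual sites could still be compared. Whether the composite would mislead depends on how those trials define theirs, which the protocol does not say. Likewise, the body composition results in V.D may mean DXA only. Both are fair limits on what is at stake. The protocol also defines no central-to-peripheral ratio or difference, so those examples show scale and not an error in a planned result.

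**Conclusion.** The concern holds. The scoring rule is inconsistent as written: three separately landmarked central sites are divided by two, and three peripheral sites by three, without explanation.

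On the assumption that a three-site mean is intended, every central score is exactly 50% too high. That is the more natural reading, given the parallel peripheral formula and the count of six sites, but the sponsor has to confirm it. On the alternative that two sites were meant, the excess varies by child: 33% to 80% in the illustrative cases above.

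No stated aim or planned analysis is affected. Exposed are the absolute central values, the level of any ratio or difference formed from the two scores, and any comparison or publication that uses the central composite. It should be corrected because it is an operative derivation rule and the correction is nearly free.

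**What to change.** 1. Check the intended central sites and divisor against the laboratory's standardized procedure.
2. If a three-site mean is intended, change the central divisor from two to three. If the site list is wrong, correct the list.
3. State that each score is the mean of its named sites.
4. If any central scores have already been derived with divisor two, recompute them from the stored site readings.
5. As a lesser item, give one fixed rule for the third skinfold reading. The median of three would do; so would the mean of all three, or the closest pair with a tie rule.

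The cost is a one-word or one-phrase protocol correction, one added sentence for the third reading, and a re-run of one derived variable if scores already exist. No new data collection is needed.
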